5.3 Derived Dates

Derived dates for defining analysis periods are defined as follows:

- OP start date/time: Earliest complete date during the screening epoch in the eDiary.
- OP end date/time: Latest complete date during the screening epoch in the eDiary.
- LTT start date/time: Earliest complete date during the treatment epoch in the eDiary.
- LTT end date/time: Latest complete date during the treatment epoch in the eDiary.
- Study drug first dose date/time: Earliest complete date where subjects indicated that they took medication during the treatment epoch in the eDiary.
- Study drug end dose date/time: Latest complete date where subjects indicated that they took medication during the treatment epoch in the eDiary.
- Study drug last dose date/time: Study drug end dose date derived only for subjects who have non-missing completion status on the Study Exit Status CRF. Thus, in an interim analysis, all post-treatment data will be included for a subject who is still on study. At the last database lock, the last dose date will be equal to the end dose date for treated subjects.
- EOT visit date: Maximum of the following: (1) LTT end date/time; (2) latest complete visit date excluding folder name “follow-up safety visit” on the Visit Date CRF. This is derived only for subjects who have non-missing completion status on the Study Exit Status CRF.

- Last contact date: (1) Complete death date, if it exists; (2) otherwise, the maximum complete date of the following: AE start/stop; ECG; eDiary; enrollment; informed consent; laboratory collection; non-study medication start/stop; physical measurement; procedure; rating scale; questionnaire; screening; study completion/discontinuation; vital sign; visit.

No imputations are performed on these derived dates. Complete dates are those with valid, non-missing day, month, and year.

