# 4.3.4 Follow up Safety Visit

Patients will return to the study site 14 days after the Week 12/52/EOT Visit (+/- 2 days) to collect laboratory tests, vital signs, electrocardiography, and AEs. Investigators should assess patients for AEs consistent with drug dependency or withdrawal effects and report as appropriate (see Section 7.4).

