## 8.2.1 Collection and Reporting of Non-Serious Adverse Events

The collection of non-serious AE information should begin at the initiation of study drug. Non-serious AE information should also be collected from the start of a placebo lead-in phase or other observational period intended to establish a baseline status for a patient.

Non-serious adverse events should be followed until conclusion or stabilization, ore reported as SAEs if they become serious. Follow-up is also required for non-serious AEs that cause interruption or discontinuation of study drug or those that are present at the end of study treatment.

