- Enrollment to last visit during LTT: $100 * (\text{total number of data days from the IWRS enrollment date to the last visit date during LTT}) / (\text{Last visit date during LTT} - \text{IWRS enrollment date} + 1)$. Last visit date during LTT is same as EOT visit date, but derived for all treated subjects (see Section 5.3).

eDiary compliance will be summarized as a continuous parameter and as the number and percentage of subjects in the following categories: $\geq 90\%$ compliance; $\geq 80\%$ compliance. Subject sources are the evening report, PoM, and SM. The site source is the medication reconciliation form.

Drug Accountability Compliance

Drug accountability compliance will be summarized by enrollment group and overall with the number and percentage of enrolled subjects in the following categories:

- At least one kit dispensed
- Did not return at least one kit dispensed and discontinued the study
- Did not return any kit dispensed and discontinued the study.

Kit dispensed and kit returned will be identified from “yes” responses to the questions “was this kit dispensed” and “was this kit returned”, respectively.

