5.4 Analysis Periods

Analysis periods are defined as follows:

- Observational Period (OP): measurement date/time on or after the OP start date/time through the OP end date/time. This period is used to assess the number of migraine days per 4 weeks during the OP.
- Pre-treatment: measurement date/time on or before the study drug first dose date/time. This period is used to derive baseline values, and to assess safety and outcomes research endpoints.
- Post-enrollment: measurement date/time after the IWRS enrollment date/time through the EOT visit date + 7 days. This period is used to derive analysis visit windows for slotting observations.
- Follow-up: measurement date after the EOT visit date + 7 days. This period is used to slot observations.
- Long-term treatment (LTT): measurement date/time on or after the LTT start date/time through the LTT end date/time. This period is used to assess the number of migraine days per 4 weeks and number of tablets taken during LTT.
- On-treatment safety: measurement date/time after the study drug first dose date/time through the study drug last dose date + 7 days. Note that AEs with imputed start date equal to the study drug first dose date are part of this period (refer to the BHV3000 Core SAP for AE start date imputation). This period is used to assess safety endpoints on treatment.
- Follow-up safety: measurement date after the study drug last dose date + 7 days. This period is used to assess safety endpoints during follow-up.

See Section 5.3 for derived dates for determining analysis periods. If measurement time is missing or not collected, then the measurement date will be compared to the derived date.

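### A post-treatment unscheduled visit can move the derived EOT date and shift the follow-up visit's by-visit values from the Follow-up Week 2 row to Follow-up EOT

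*SAP*

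**What the plan says.** SAP 5.3 gives the derivation: "EOT visit date: Maximum of the following: (1) LTT end date/time; (2) latest complete visit date excluding folder name" follow-up safety visit, as recorded on the Visit Date CRF. Unscheduled visits are not mentioned.

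SAP 5.4 uses this date to separate the two periods that drive visit slotting:
- "Post-enrollment: measurement date/time after the IWRS enrollment date/time through the EOT visit date + 7 days"
- "Follow-up: measurement date after the EOT visit date + 7 days"

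SAP 5.5 counts follow-up days from the same date and sets Follow-up Week 2 at follow-up days 8 to 21.

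The safety periods in SAP 5.4 are anchored differently. On-treatment safety is "measurement date/time after the study drug first dose date/time through the study drug last dose date + 7 days", and the other period is "Follow-up safety: measurement date after the study drug last dose date + 7 days".

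SAP 4.8 assigns by-visit safety values first to visit windows and then to safety periods. The latest value in a Week 2 to Week 56 window that lies in the follow-up safety period is printed under Follow-up EOT.

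SAP 4.8.1 (eDiary Compliance) reuses the date: "Last visit date during LTT is same as EOT visit date".

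Protocol 4.3.4 times the follow-up visit: "Patients will return to the study site 14 days after the Week 12/52/EOT Visit (+/- 2 days".

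**The concern.** The derivation is meant to find the end-of-treatment visit, but it finds the last dated visit in any folder except one. SAP 4.8.1 describes the result as the last visit during long-term treatment, and a visit after treatment has ended does not fit that description. SAP 5.5 also has a Follow-up Week 4 row, so measurements well after EOT are expected. Yet a late visit in any other folder resets EOT to its own date and so cannot be slotted as follow-up.

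Visits after EOT are plausible. Protocol 8.2.1 says "Follow-up is also required for non-serious AEs that cause interruption or discontinuation of study drug or those that are present at the end" (meaning when treatment stops), Protocol 8.1.2 has SAEs followed to resolution or stabilization, and Protocol 8.1.5 wants liver abnormalities confirmed promptly. None of these states that a clinic visit is made or which CRF folder it would use.

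At stake is whether the Follow-up Week 2 row of the by-visit tables contains the follow-up visit for every subject who attended it, and whether one compliance figure uses the right denominator.

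**Working it through.** The plan states no figure to reproduce; the check is date arithmetic on SAP 5.3 to 5.5.

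**Inputs**
- f = days from true EOT to the scheduled follow-up visit: 14, range 12 to 16 (Protocol 4.3.4).
- d = days from true EOT to the latest other visit on the Visit Date CRF. This is an assumption; the documents do not give it.
- Derived EOT = true EOT + d (SAP 5.3).
- The follow-up visit is slotted as post-enrollment if f ≤ d + 7, that is, d ≥ f − 7 (SAP 5.4).
- Illustrative true EOT: study day 365 (52-week) or 85 (12-week).

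**Threshold and resulting window (SAP 5.5, Tables 5 and 6)**

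| f | Misfiled when d is at least | 52-week: study day, window | 12-week: study day, window |
|---|---|---|---|
| 12 | 5 | 377, Week 52 | 97, Week 12 |
| 13 | 6 | 378, Week 52 | 98, Week 12 |
| 14 | 7 | 379, Week 56 | 99, Week 16 |
| 15 | 8 | 380, Week 56 | 100, Week 16 |
| 16 | 9 | 381, Week 56 | 101, Week 16 |

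Example: EOT Day 365, recheck Day 372, follow-up visit Day 379. Derived EOT + 7 = 379. The visit is not after that day, so it goes to Week 56. Any other visit later than the follow-up visit also meets the condition. Below the threshold EOT moves, but the follow-up visit stays in Follow-up Week 2.

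**Which safety period?** Take last dose as no later than true EOT (unused drug is returned then, Protocol 4.3.3). The follow-up visit is then at least 12 days after last dose. Since 12 > 7, it is always in follow-up safety and never on-treatment.

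**Which row?** Under SAP 4.8 its value prints under Follow-up EOT if it is the latest such value. It may displace the real EOT value there when that value is also more than 7 days after last dose, which can happen under as-needed dosing. The parameters affected are those scheduled at the follow-up visit and summarized by visit: LFTs, vital signs and ECG (Protocol Tables 1 and 2; SAP 4.8.3 to 4.8.5).

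**Compliance, enrollment to last visit.** With a complete diary to true EOT on study day L, compliance = 100 × L / (L + d).
- L = 85, d = 7: 85/92 = 92.4%
- L = 85, d = 10: 85/95 = 89.5%
- L = 365, d = 7: 365/372 = 98.1%
- L = 365, d = 10: 365/375 = 97.3%

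The SAP's 90% category is lost once L + d > L/0.9. For L = 85 that is 94.4, so d ≥ 10. For L = 365 it is 405.6, so d ≥ 41.

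**With d = 0** (EOT not moved), a follow-up visit at f = 12 to 16 falls on follow-up days 13 to 17. That is later than EOT + 7 and inside the 8 to 21 window, so it is always Follow-up Week 2.

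**The case against.** The strongest reply is that the derived EOT date only slots observations. AEs, LFT elevations, eDISH plots, worst laboratory grades, S-STS, vital-sign and ECG abnormalities and the follow-up population all depend on last dose + 7 days. SAP 4.8 also provides a follow-up row for the displaced value. All of this stands. A reader might infer that the follow-up visit is counted as on-treatment, or that a primary or secondary endpoint changes; the documents support neither.

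The premise is also unverified. The unscheduled visits that the documents name are for dispensing drug, which does not apply after EOT. LFTs are already scheduled about 14 days after EOT, and prompt confirmation of a liver abnormality could fall before the threshold. If post-EOT rechecks are not entered on the Visit Date CRF, the problem does not arise. This limits the size of the point. It does not repair the rule, which has no exclusion for such visits.

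A further tempting inference is that subjects with abnormal results drop out of Follow-up Week 2 selectively, so that the row looks more reassuring. That is possible but not shown. No reasons for post-EOT visits are given, and removing a value that had already normalised would not flatter the row. Nor are all laboratory tests involved: the schedules list only LFTs among the blood safety tests at the follow-up visit.

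On compliance, the measure is one of four descriptive ones. The effect is small for the roughly 1800 planned 52-week subjects (1200 + 600).

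**Conclusion.** The point holds as a minor error of derivation. Taken literally, SAP 5.3 lets a dated visit after EOT in any folder other than the follow-up safety visit become the EOT date. At 7 days or more after true EOT (5 to 9 across the tolerance), the scheduled follow-up visit moves out of Follow-up Week 2.

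The effect is confined to two places: the row in which LFT, vital-sign and ECG values appear in by-visit summaries, and one compliance denominator, where it matters mainly for 12-week subjects.

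This rests on two assumptions: that such visits occur, and that they are entered on the Visit Date CRF in a separate folder. Their number cannot be derived from the documents. For scale only, each 1% of about 2000 subjects is 20 subjects.

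**What to change.** In SAP 5.3, item (2) of the EOT visit date, exclude unscheduled-visit folders dated after the Week 12/52 or early-termination visit, in addition to the follow-up safety visit. If that visit is missing, exclude those dated after the last scheduled treatment visit. Keep the maximum with the LTT end date, so that diary days recorded after the visit are still covered. For duplicate subjects (SAP 5.1.2), take the latest qualifying visit across all identifiers.

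Post-EOT rechecks that then fall in the Follow-up Week 2 window are handled by the existing closest-to-target rule in SAP 4.8.

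The cost is one sentence in the SAP, a small change to the derived-date program, and a check of the folder names on the Visit Date CRF. No data collection changes.

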5.4 Analysis Periods

Analysis periods are defined as follows:

- Observational Period (OP): measurement date/time on or after the OP start date/time through the OP end date/time. This period is used to assess the number of migraine days per 4 weeks during the OP.
- Pre-treatment: measurement date/time on or before the study drug first dose date/time. This period is used to derive baseline values, and to assess safety and outcomes research endpoints.
- Post-enrollment: measurement date/time after the IWRS enrollment date/time through the EOT visit date + 7 days. This period is used to derive analysis visit windows for slotting observations.
- Follow-up: measurement date after the EOT visit date + 7 days. This period is used to slot observations.
- Long-term treatment (LTT): measurement date/time on or after the LTT start date/time through the LTT end date/time. This period is used to assess the number of migraine days per 4 weeks and number of tablets taken during LTT.
- On-treatment safety: measurement date/time after the study drug first dose date/time through the study drug last dose date + 7 days. Note that AEs with imputed start date equal to the study drug first dose date are part of this period (refer to the BHV3000 Core SAP for AE start date imputation). This period is used to assess safety endpoints on treatment.
- Follow-up safety: measurement date after the study drug last dose date + 7 days. This period is used to assess safety endpoints during follow-up.

See Section 5.3 for derived dates for determining analysis periods. If measurement time is missing or not collected, then the measurement date will be compared to the derived date.

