### 5. ECG and Laboratory Test Findings

- a) Estimated glomerular filtration rate (eGFR) according to the re-expressed abbreviated (four-variable) Modification of Diet in Renal Disease (MDRD) Study equation ≤ 40 ml/min/1.73m
- b) Corrected QT interval > 470 msec (QTc by method of Frederica), at Screening
- c) Left Bundle Branch block
- d) Right Bundle Branch Block with a QRS duration  $\geq 150$  msec.
- e) Intraventricular Conduction Defect with a QRS duration ≥ 150 msec.

- f) Serum bilirubin (Total, Direct or Indirect) bilirubin > 1 x ULN (Only abnormal values of between 1-1.5x ULN may be repeated once for assessment of eligibility during the screening period.)
- g) Neutrophil count  $\leq 1000/\mu L$  (or equivalent).
- h) AST or ALT > 1 x ULN (Only abnormal values of between 1-1.5x ULN may be repeated once for assessment of eligibility during screening period.)
- i) HbA1c > 6.5%

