For screened subjects who were not enrolled, baseline is defined as the last non-missing value available. For enrolled subjects who were not treated, baseline is defined as the last non-missing value on or before the IWRS enrollment date/time. For treated subjects, baseline is defined as

the last non-missing value on or before the study drug first dose date/time (i.e., in the pre-treatment analysis period; see Sections 5.3 and 5.4).

Age (years) at informed consent is calculated as: (informed consent date - birth date + 1) / 365.25.

For migraine history, time since last migraine (days) is calculated as informed consent date – imputed last migraine date for subjects with imputed last migraine date up to 1 year before informed consent date. Last migraine dates will be imputed for partial and missing dates using the same methodology as for imputation of AE start dates, but using the informed consent date as the surrogate date. Refer to the BHV3000 Core SAP for AE start date imputation.

For each subject, multiple medical histories of the same SOC or PT will be counted only once within each SOC and PT. Medical histories will be presented in descending order of overall frequency within SOC and PT.

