4.6.3 Exploratory Safety and Other Endpoints

4.6.3.1 LFT Elevations

The number and percentage of subjects with LFT elevations will be summarized separately for the following populations and safety analysis periods:

- Screened subjects during pre-treatment by enrollment group, and overall
- Treated subjects during pre-treatment by enrollment group and overall
- Treated subjects on-treatment by enrollment group and overall
- Treated subjects on-treatment by subgroup level and overall for all subgroups of interest specified in Section 4.2.6
- Treated subjects on-treatment by enrollment group and overall for subjects who did not participate in previous Studies BHV3000-301/302/303
- Follow-up subjects during follow-up by enrollment group and overall.

LFT elevations include the following endpoints:

- Cumulative elevations:
 - ALT $> 1 \times, > 3 \times, > 5 \times, > 10 \times$, and $> 20 \times$ ULN
 - AST $> 1 \times, > 3 \times, > 5 \times, > 10 \times$, and $> 20 \times$ ULN
 - ALT or AST $> 1 \times, > 3 \times, > 5 \times, > 10 \times$, and $> 20 \times$ ULN
 - TBL $> 1 \times, 1.5 \times$, and $> 2 \times$ ULN
 - Alkaline phosphatase (ALP) $> 1 \times, > 1.5 \times$, and $> 2 \times$ ULN

- Mutually exclusive elevations:
 - ALT > ULN to $\leq 3 \times$ ULN, $> 3 \times$ ULN to $\leq 5 \times$ ULN, $> 5 \times$ ULN to $\leq 10 \times$ ULN, $> 10 \times$ ULN to $\leq 20 \times$ ULN, and $> 20 \times$ ULN
 - AST > ULN to $\leq 3 \times$ ULN, $> 3 \times$ ULN to $\leq 5 \times$ ULN, $> 5 \times$ ULN to $\leq 10 \times$ ULN, $> 10 \times$ ULN to $\leq 20 \times$ ULN, and $> 20 \times$ ULN
 - ALT or AST > ULN to $\leq 3 \times$ ULN, $> 3 \times$ ULN to $\leq 5 \times$ ULN, $> 5 \times$ ULN to $\leq 10 \times$ ULN, $> 10 \times$ ULN to $\leq 20 \times$ ULN, and $> 20 \times$ ULN
- Composite elevations:
 - ALT or AST $> 3 \times$ ULN and TBL $> 1.5 \times$ ULN
 - ALT or AST $> 3 \times$ ULN and TBL $> 2 \times$ ULN
 - ALT or ALT $> 3 \times$ ULN concurrent with TBL $> 2 \times$ ULN with Agresti-Coull 95% CIs (see Section 4.6.2)
 - ALT or ALT $> 3 \times$ ULN concurrent with TBL $> 2 \times$ ULN and ALP $\leq 2 \times$ ULN with Agresti-Coull 95% CIs (see Section 4.6.2)
 - ALT or AST $> 3 \times$ ULN concurrent with AEs of interest (nausea, vomiting, anorexia, abdominal pain, fatigue; see Section 4.6.3.2).

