Rates of multiple on-treatment, cumulative and mutually exclusive LFT elevations will be summarized using descriptive statistics for treated subjects (1) enrollment group and overall, and (2) subgroup level and overall for key extrinsic exposure factors. For each subject and LFT elevation endpoint, the rate is defined as total number of elevations/total number of non-missing values during the on-treatment period. Multiple values on the same collection date will be counted only once.

The number and percentage of subjects with time to first on-treatment LFT elevations ($ALT > 3 \times ULN$; $AST > 3 \times ULN$; ALT or $AST > 3 \times ULN$) will be presented by enrollment group and overall for treated subjects with on-treatment LFT elevations in the following categories: ≤ 2 , > 2 to ≤ 4 , > 4 to ≤ 8 , ..., > 48 to ≤ 52 , > 52 weeks. Time to elevation is calculated as $(LFT \text{ collection date} - \text{study drug first dose} + 1)/7$.

In all of these analyses described in this section, subjects must have non-missing LFT data (i.e., ALT , AST , TBL , or ALP) in the safety analysis period to be included.

4.6.3.2 *ALT or AST > 3 x Upper Limit of Normal (ULN) Concurrent with Nausea, Vomiting, Anorexia, Abdominal Pain or Fatigue*

AST or $ALT > 3 \times ULN$ elevations that are concurrent with nausea, vomiting, anorexia, abdominal pain or fatigue will be summarized, as the number and percentage of subjects experiencing this concurrently, in the same table as other LFT elevation endpoints described in Section 4.6.3.1. For a given safety analysis period (pre-treatment, on-treatment, follow-up), an LFT elevation is concurrent with an AE of interest if the imputed AE start date is $+\/- 7$ days inclusive of the LFT collection date; both the LFT collection date and the imputed AE start date must also be in the safety analysis period. Refer to the BHV3000 Core SAP for AE start date imputation. The following will be used to identify the AEs of interest: nausea, vomiting, anorexia, fatigue, and those containing “abdominal pain”.

4.6.3.3 *LFT Elevations by Gender, Age, and Rimegepant Exposure*

See Section 4.6.3.1.

4.6.3.4 *Secondary Safety Endpoints by Rimegepant Exposure*

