4.8.2 Adverse Events

Refer to the BHV3000 Core SAP for AE start date imputation, AE counting rules, definition of treatment-emergent adverse events (TEAEs), and definition of AEs related to study drug.

Tables will present the number and percentage of subjects experiencing AEs by SOC and PT, unless specified otherwise.

A by-subject listing of all AEs will be provided for screened subjects that will flag on-treatment and treatment-emergent AEs. Additional by-subject listings of deaths, SAEs, AEs leading to study drug discontinuation, hepatic-related AEs, and AEs of special interest (i.e., potential drug abuse, CV, and suicidality) will be provided for screened subjects. Refer to the BHV3000 Core SAP for listing content and AEs of special interest.

AE Overview

An AE overview without SOC and PT will present the number and percentage of subjects with any the following AEs: any AE; severe AE; AE related to study drug (unlikely related, possibly related, or related); SAE; SAE related to study drug; AE leading to study drug discontinuation; AE leading to death; hepatic-related AE; severe hepatic-related AE; hepatic-related SAE; hepatic-related AE leading to study drug discontinuation; potential drug abuse AE; CV AE; suicidality AE. An AE overview will be produced for each the following analysis periods and populations:

- Pre-treatment AEs for screened subjects by enrollment group and overall
- Pre-treatment AEs for treated subjects by enrollment group and overall
- TEAEs for treated subjects by enrollment group and overall
- On-treatment AEs for treated subjects by enrollment group and overall
- On-treatment AEs for treated subjects by subgroup level and overall for all subgroups of interest specified in Section 4.2.6
- Follow-up AEs for follow-up subjects by enrollment group and overall.

Pre-Treatment AEs

Pre-treatment AEs will be summarized by SOC and PT by enrollment group and overall for screened subjects for the following endpoints:

- AEs
- SAEs.

Pre-treatment AEs will be summarized by SOC and PT for treated subjects by enrollment group and overall for the following endpoints:

- AEs by severity (total, mild, moderate, severe, moderate or severe, not reported)
- SAEs.

On-Treatment AEs

On-treatment AEs will be summarized by SOC and PT for treated subjects by enrollment group and overall for the following endpoints:

- AEs by severity*
- TEAEs by severity

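### SAP 5.4 places adverse events that start on the first-dose date in both the pre-treatment and the on-treatment period

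*SAP*

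**What the plan says.** SAP 5.4 (Analysis Periods) sets the boundary at the first dose. The earlier period is "Pre-treatment: measurement date/time on or before the study drug first dose date/time". 5.4 says it serves to derive baseline and also to assess safety and outcomes research endpoints. On-treatment safety covers measurements after the first dose date/time, up to 7 days after the last dose date. One exception is attached to it: "Note that AEs with imputed start date equal to the study drug first dose date are part of this period". For values without a clock time, the rule is "If measurement time is missing or not collected, then the measurement date will be compared to the derived date".

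SAP 4.8.2 (Adverse Events) plans pre-treatment AE tables for two populations. For screened subjects there is an overview ("Pre-treatment AEs for screened subjects by enrollment group and overall") plus AEs and SAEs. For treated subjects there is an overview, AEs by severity and SAEs. On-treatment tables follow separately. SAP 4.6.3.1 (LFT Elevations) plans a liver function test (LFT) table for "Screened subjects during pre-treatment by enrollment group, and overall".

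SAP 5.3 (Derived Dates) takes the first dose date from eDiary dosing records and does not impute it. SAP 4.4.1 (Subject Disposition) identifies enrolled but untreated subjects by the absence of a dose start date.

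**The concern.** For laboratory values the two periods do not overlap: one ends at the first dose and the other begins after it. The exception breaks this for AEs. It adds events of the first-dose date to on-treatment, but the pre-treatment entry carries no matching exclusion, and no sentence says that the periods exclude each other for AEs. AEs are placed by imputed start date, so a date-only comparison is the expected case.

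At stake is the content of the pre-treatment AE overview, severity and SAE tables. A reaction to the first tablet would appear there as an event from before treatment. The pre-treatment count of ALT or AST above 3 x ULN concurrent with symptoms could also be touched: SAP 4.6.3.2 requires the symptom start and the LFT date to lie in the same period and within 7 days of each other, so nausea on the first-dose date could be paired with a pre-dose LFT. Two programmers working from 5.4 could produce different tables.

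A smaller gap sits in the same sentence. Subjects who were screened but never dosed have no first dose date, so 5.4 gives no reference point for their data, although pre-treatment AE, SAE and LFT tables are planned for screened subjects.

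**Working it through.** The plan states no figure on this point. The check applies the 5.4 rules as written, with dates only, to events around the first-dose date (day 0).

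| Event | 5.4 as written | With the fix |
|---|---|---|
| AE, day -1 | pre-treatment | pre-treatment |
| AE, day 0 | pre-treatment and on-treatment | on-treatment |
| AE, day +1 | on-treatment | on-treatment |
| Laboratory value, day -1 | pre-treatment | pre-treatment |
| Laboratory value, day 0 | pre-treatment | pre-treatment |
| Laboratory value, day +1 | on-treatment | on-treatment |
| Any event, never dosed | cannot be assigned | pre-treatment |

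Only two rows change. The overlap is confined to AEs on day 0. Laboratory values keep their period, so baseline does not move.

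**Illustrative size for the treated-subject table.** Inputs: about 2000 treated subjects (the planned number assigned, Protocol 5.1); b = proportion with a true pre-treatment AE, assumed 8-16%; a = proportion with an AE starting on day 0, assumed 0.5-3%. Neither a nor b is given in the documents. If the two occur independently within subjects, and each subject counts once, the pre-treatment percentage rises by a x (1 - b).

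- b = 16%, a = 0.5%: 0.5 x 0.84 = 0.42 points; 0.0042 x 2000 = about 8 subjects; 0.42/16 = 3% relative.
- b = 8%, a = 0.5%: 0.5 x 0.92 = 0.46 points; about 9 subjects; 0.46/8 = 6% relative.
- b = 16%, a = 3%: 3 x 0.84 = 2.52 points; about 50 subjects; 2.52/16 = 16% relative.
- b = 8%, a = 3%: 3 x 0.92 = 2.76 points; about 55 subjects; 2.76/8 = 35% relative.

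**Never-dosed subjects.** Protocol 5.1 foresees about 2800 screened and up to about 2000 assigned: 2800 - 2000 = 800, and 800/2800 = 28.6%. Subjects enrolled but never dosed would add to this.

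**The case against.** The strongest reply is that the note is a specific rule for a tie. Without it, the general rule would put day-0 AEs in pre-treatment, so its natural purpose is to move them. SAP 4.8.2 also treats pre-treatment, on-treatment and follow-up as successive periods when it combines them. That is probably the intent, but the text says only that these AEs belong to on-treatment, not that they leave pre-treatment. 4.8.2 refers AE counting rules, start-date imputation and the treatment-emergent definition to the BHV3000 Core SAP, which could settle the matter. That limit stands.

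A reader might infer that the error distorts the main safety comparison. The documents do not support this. The primary and secondary estimands (SAP 2.3.1 and 2.3.2) concern treated subjects, their laboratory and discontinuation components are specified on treatment, and SAP 4.6.1 and 4.6.2 tabulate the AE endpoints on treatment, where day-0 AEs count under either reading. No section calls the pre-treatment tables the reference for AE or LFT frequency. The combined-period discontinuation tables count subjects, so they do not count anyone twice.

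A reader might also infer that data of never-dosed subjects are lost, and that the screened LFT table shrinks to the treated one, because "subjects must have non-missing LFT data" in the period to be included and those left out would include subjects excluded for "AST or ALT > 1 x ULN". That goes too far. A subject who took no drug has only pre-treatment data. Screened and treated tables are listed separately, which would be pointless if they held the same events. SAP 4.5 shows the intent for baseline: "For screened subjects who were not enrolled, baseline is defined as the last non-missing value available". The by-subject listings of AEs, SAEs and LFT values for screened subjects (4.8.2 and 4.8.3) would still show these data. Nor can a diluted AE rate for screened subjects be derived: those who fail at the screening visit have little observation time, and the documents give no split.

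**Conclusion.** The point holds for AEs on the first-dose date. As written, SAP 5.4 assigns them to both periods, so the descriptive pre-treatment AE and SAE tables would include first-dose-day reactions. The increase is about 0.4-2.8 percentage points (8-55 of 2000 subjects) under the assumed rates. That range reflects the chosen inputs and is not an estimate for this trial. The conclusion rests on date-only comparison and on the Core SAP containing no tie-break. An AE with a recorded start time after the dose would be on-treatment only. No primary, secondary or other on-treatment result changes.

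The missing rule for never-dosed subjects is a minor gap in wording whose intent is easy to infer. It is worth closing in the same edit, but it is not evidence that data would be discarded.

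**What to change.** Reword the pre-treatment entry in SAP 5.4 along these lines: 'Pre-treatment: for AEs, imputed start date earlier than the first dose date; for all other measurements, the present rule unchanged; for screened subjects who were never treated, all measurements.' Keep the on-treatment note as it is. If the Core SAP already contains a tie-break, cite it in 5.4 and make sure that the two agree.

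One consequence should be accepted openly: an AE that began on the first-dose date but before the tablet would be reported as on-treatment only. It is already counted there under the note, so on-treatment tables do not change.

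The cost is one sentence and the matching derivation code. No new data are needed.
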